8.3.5 Subgroup analyses

Besides the subgroup analyses described in the secondary objectives, safety results will be analyzed by weight and age characteristics. Additionally, anemia-related results will be analyzed by Schistosomiasis and malaria co-infection status.

8.3.6 Multiplicity and Missing Data

An interim analysis is planned at week 16 for the efficacy endpoints of cure rate and egg reduction rate after PZQ administration and single and repeated courses of AM. The endpoints of interest will be analyzed and communicated as soon as the data is collected and cleaned. The analysis and results will not influence follow-up or analysis of the rest of the objectives and endpoints in any way.

The primary analysis is a comparison of a single measurement, thus no adjustments for multiplicity are needed.

Subjects who do not attend all treatment administration visits or the follow-up visits will be considered as missing and will be excluded from the per-protocol analysis. No imputation of missing data will be performed.

9. MONITORING AND QUALITY ASSURANCE

This study will be monitored in accordance with regulations applicable to clinical trials, including ICH-GCP and WHO-GCLP, and sponsor-specific SOPs. The PI and involved site research staff will allocate adequate time and resources for such monitoring activities. The investigator will also ensure that the monitor or QA reviewer is given access to all the above noted study-related documents and study-related facilities (e.g. pharmacy, diagnostic laboratory, etc.) and has adequate space and resources to conduct monitoring and source data verification.

Monitoring will be performed by the Clinical Research Scientist (CRS) of the ITM Clinical Trial Unit (CTU) and the Institut de Recherche en Santé, de Surveillance Epidémiologique et de Formation (IRESSEF). A monitoring plan will be written to detail the frequency, requirements content, percentage of Source Data Verification (SDV) of study monitoring visits. Findings from monitoring visits will be noted in a visit report that will be shared with the study team.

Monitoring visits of the CTU CRS will be combined with supervision visits of other members of the sponsor study team. These visits will also contribute to the quality assurance of the study and will be documented in a visit report.

All laboratory procedure will be carried out according to SOPs developed by the study team and quality control (QC) procedures will be followed for all laboratory techniques in the study site and at ITM.

The sponsor will inform the Investigators concerned immediately upon notification of a pending study inspection by any regulatory authority or funder. Likewise, the investigator will inform the sponsor of any pending inspection.

10. DATA MANAGEMENT

Full details regarding the handling of trial data will be described in the trial Data Management Plan (DMP). The DMP describes the lifecycle for the data to be collected, processed and/or generated and includes information on how data will be collected, processed, shared, curated, preserved and includes the methodologies and standards applied.

Responsibilities

The data manager at the ITM's CTU will be responsible for setup of the eCRF/database, system validation and management, change control, drawing up the data management plan and any other essential data management documentation such as data entry guidelines, validation file, etc.

During the study, the monitor will visit the investigational site to confirm that data are being accurately recorded in the eCRFs from the subject source documents, i.e. source data verification (SDV), as described in chapter 9.

Data collection is the responsibility of the clinical trial staff at the site under the supervision of the site investigator. The investigator is responsible for ensuring the accuracy, completeness, legibility, and timeliness of the data reported.

Data collection and quality

All source documents should be completed in a neat, legible manner to ensure accurate interpretation of data. Data recorded in the electronic case report form (eCRF) derived from source documents should be consistent with the data recorded on the source documents, or discrepancies should be explained. Only data defined by the study protocol should be captured in the eCRF. In addition to paper source, some data will be entered directly in the electronic CRF.

Clinical data (including adverse events (AEs) and concomitant medications) and clinical laboratory data will be entered into eCRFs using a ICH-GCP compliant data capture system, REDCap. For practical reasons, data collection on site will be done with the REDCap Mobile App using tablets, while data management will be done using the web application. The data system includes password protection and internal validation checks to identify data that appear inconsistent, incomplete, or inaccurate. Data modifications will be automatically tracked by an audit trail detailing the date and time of the correction and the name of the person making the correction. The system will be validated before moved to production and taken into use. A data dictionary containing metadata and SOP for using the system will be maintained.

Confidentiality and security

All participant related information will be kept strictly confidential. All records will be kept in a secure location and only research staff will have access to the records.

All personal data collected in the eCRF and study database will be pseudonymized, by which a unique trial specific code will be assigned to each study participant. Any information that could lead to the identification of the participant will not be included in the study data electronic file.

The eCRF is only accessible via a login with personal username and password. Trial team members will be given user rights based on their study role and a list of authorized users will be kept at the CTU and updated regularly. Data backups will be maintained on the ITM server.

Record retention and archiving

Data management documentation (DMP, Validation File, metadata, SOP for data entry, user list, training log) will be stored electronically in an access-controlled study-specific folder on the ITM server; paper documents will be kept in a study-specific binder at the CTU.

The eCRF system and the database will be hosted at the ITM. After the trial database is locked and released to the statistician, a final copy of the database will be stored at the Sponsor. The IRESSEF will also receive a copy of the trial site's final and locked data as write-protected PDF-files. The PDF-files will be stored on a USB flash drive and will be provided to the Investigator. The Investigator should retain all source documents for each participant in the study, as well as all other essential trial documents.

11. ETHICAL ISSUES

11.1. Ethical and regulatory review

Ethical approval: The initial protocol and informed consent documents, as well as any further substantial amendments, will be submitted for ethical approval in the sponsor country, as well as the study country. The concerned Ethics Committees (ECs) are:

- The Institutional Review Board (IRB) of the ITM, Antwerp, Belgium
- The EC of the Antwerp University Hospital, Belgium
- The National Ethics Council for Research in Health (CNERS) in Senegal

Regulatory approval: The initial protocol and informed consent documents, as well as any further study documents and substantial amendments, will be submitted in French for regulatory approval to the competent authorities in the study country, the Ministry of Health in Senegal.

No study-specific interventions will take place before written approval by all Ethics Committees above has been obtained and the local regulatory requirements have been complied with, and the signature of the clinical study protocol of each contractual party involved have been obtained.

The study will be carried out according to the principles stated in the Declaration of Helsinki, all applicable regulations and according to the most recent GCP and GCLP guidelines.

The study will also be included in the Clinicaltrials.gov public registry prior to the start of participant recruitment.

11.2. Protocol amendments

Once the final clinical study protocol has been issued and signed by the authorized signatories, it cannot be informally altered. Protocol amendments have the same legal status and must pass through the appropriate steps before being implemented. Any substantial change must be approved by all the bodies and EC's that have approved the initial protocol, prior to being implemented, unless it is due to participant's safety concerns (in which case the immediate implementation can be necessary for the sake of participant's protection). In case modifications to the protocol or amendment are requested by any local EC/CA during the review process, these must be discussed and agreed upon with the Sponsor prior to any resubmission incorporating those changes.

11.3. Informed consent

No participant may be admitted into the study until the Investigator or designee has obtained the written informed consent of the parents/guardian, and verbal consent (assent) from the participating child.

Details for obtaining informed consent and assent are described in detail in chapter 5.2.

Participation in this trial is entirely voluntary. Any participant (children or his/her parent(s) or legal guardian) may withdraw from the study at any time without this decision affect the medical advice and care provided.

11.4. Confidentiality and data protection

Personal and medical information from the trial will be kept confidential, in line with the requirements of the European General Data Protection Regulation 2016/679, and with applicable requirements in Senegal. Each study participant will be given a unique study-specific participant code and personal identifiers will not appear on the Case Report Forms, the database, or the biological samples, which

will be pseudonymized from the beginning of the collection process. Access to all paper and electronic study files will be restricted to authorized study staff. Study computers and databases will be username and password-protected. Electronic datasets during the study will be shared on secure platforms. All documents that may identify the participants, e.g., signed informed consent forms, original hospital and laboratory records, identification logs, etc., will only be stored at the study sites and will not be sent to ITM.

This project involves collection and processing of personal data including biomedical, biometric, and demographic data. However, data on sexual lifestyle, political opinion, religious or philosophical conviction will not be collected. Furthermore, genetic information will not be collected. Prior data collection and processing, authorization for data and sample transfer will be asked from

Prior data collection and processing, authorization for data and sample transfer will be asked from applicable ethics and/or regulation committees of both Senegal and Belgium.

11.5. Community involvement

The first step will consist in informing administrative, medical authorities as well as community leaders about the project purpose and the design of the study. Before starting the study, a communication plan will be designed to inform the population, and most importantly the school directors and teachers, on the study procedures. Verbal permission of the head of households and school directors will be sought. Also, the health centers closest to the study schools will be invited to the kick-off meeting, to inform them about the study and train them in monitoring for expected side effects of the study medication and how to keep the study team informed about any study participant that comes to the health center, so that potential (S)AEs may be collected, and patients will be immediately and adequately treated. These local health facilities will also be regularly visited during the study to keep them focused and motivated for listing participants who have visited them

11.6 Risks and benefits

11.6.1. Risks

Minor participants

This project is built around a randomized clinical trial involving human participants who are considered as vulnerable, for at least two reasons: (1) children of school age are minors and, therefore, not entitled to make an autonomous decision on trial participation; (2) children in this trial mainly belong to socially vulnerable groups (where poor access to health care may affect voluntarism in the informed consent process, since trial participation may be primarily seen as a strategic choice to secure trial-related health and non-health benefits).

To ensure full protection of the trial participants, the trial is conducted according to strict protocols and regulations and a written informed consent will be obtained from parents or guardian (as well as assent from the children) as described in section 5.2.

Medical interventions including invasive techniques

The clinical trial involves medical interventions in human participants, i.e., a full clinical examination, anthropometric measurements, a search for signs and symptoms of chronic schistosomiasis or malaria and an ultrasound examination of organ-specific schistosomiasis morbidity. The laboratory assessments will require the collection of blood by finger prick (considered as invasive technique that might cause pain), urine and stool samples, which will be clearly mentioned and detailed in the Informed Consent Form. No other invasive or dangerous techniques are required.

All medical examinations and collections of biological samples will be carried out by adequately qualified staff in a dedicated room, ensuring the privacy and confidentiality of all participants.

Tolerance of the investigational Medical Product

The side-effects of the treatments will be discussed with the parents/guardian. Long-term experience with AM combination for malaria treatment has shown that the side effect profile is manageable, and usually better tolerated by children than by adults. Oral artesunate does not pose problems in terms of safety and tolerability. The tolerability of mefloquine is widely considered to be less than artesunate; however, it has been used as treatment in tens of thousands of malaria patients in various countries and as chemoprophylaxis for the last 30 years in travelers and pregnant women with no major problems, provided counselling is adequate and specific contra-indications are respected ^{39,40}. This drug is usually better tolerated by children than by adults ³⁹. Particular attention will be paid during screening to the classic contra-indications of mefloquine (i.e. history of epilepsy and psychiatric disturbances). Primary school children will be closely monitored for side effects, particularly during the AM courses. In case of severe intolerance (digestive or neurological), treatment will be discontinued, and the child concerned will be excluded from the trial and treated and followed up until adverse symptoms subside.

A safe interval of 6 weeks between each AM administration is proposed because some data in Asia suggest that the frequency of side effects may increase if mefloquine is reused for treatment within four weeks after a first administration ⁴⁰.

Nevertheless, a robust safety monitoring system has been set up to pro-actively scrutinize the tolerance and safety profile of (artesunate)-mefloquine. Firstly, each dose of AM will be given under direct medical observation during the three first days, with assessment of tolerance since the previous administration and possibility of immediate discontinuation based on medical decision. Toxicity of mefloquine usually appears early and is rather acute (vomiting, neurological manifestations). Second, another contact with the participant either by phone call or home visit will be organized systematically by the study team one week after the first day of AM administration to proactively capture any "delayed" side effect.

Thirdly, parents of all enrolled children will be advised to bring the study ICF whenever their children need to attend the well identified study health centers at any moment during the study period, (in particular after the first and until the next AM administration) making them easily identifiable by all local health care workers. The local staff will be involved in the study, adequately informed and specifically trained to manage and report these adverse events during the preparatory period. The local investigator (medical doctor based in Richard Toll) will be immediately contacted by phone to be informed about, and provide further advice, for any problem potentially related to the study during the whole study period. Finally, medical assessment and specific queries regarding tolerance of previous administration will take place just before each subsequent AM administration. During the preparatory visits, all practicalities of the safety monitoring procedure will be established in a detailed SOP, after discussion with all local health staff.

Side effects related to PZQ are rare but may include headache, dizziness, stomach pain, nausea, tiredness, weakness, joint/muscle pain, loss of appetite, vomiting and sweating. These side effects are usually mild and temporary and may be related to some inflammatory reactions to the dying parasites. In very rare cases, more serious side effects occur such as bloody diarrhea, fever, irregular/slow heartbeat, seizures. Those side effects are short lasting and often disappear with 48h after drug administration.

Risk of favoring malaria resistance

The risk of selecting resistant parasites is extremely unlikely (or even close to non-existing) for the following reasons:

- So far, no artemisinin or partner drug resistance has been reported in large community studies conducted in high endemic areas that have evaluated ACTs for intermittent preventive treatment or seasonal malaria chemoprophylaxis ^{90–92}.
- Malaria incidence in this area is the lowest in Senegal with less than 5 cases per 1000 inhabitants, which makes it highly unlikely that the drug can be administered to a malaria patient.
- Children with clear signs of malaria or with any sign of the disease will not be eligible, making selection pressure for AM that could lead to resistance impossible, because the drug will not come into contact with plasmodium in this situation.

Loss of confidentiality

Delegated study team members will be responsible for reporting the patient's personal details and identification code in a subject identification code list (pseudonymization). To ensure confidentiality, this list will be kept in a separate, locked cupboard together with the signed ICFs and only authorized members of the study team will have access to it. All participant information will be stored in locked filing cabinets in areas with access limited to study site staff. All participant information and laboratory specimens, including stored specimens, reports, study data collection, process, and administrative forms will be identified by the study code, date of sample collection and type of study visit. Also, clinical data that is directly captured electronically in the field will only use the patient-specific study code. Names will not be used in the electronic database, nor in any written or oral report. The database will be secured with password-protected access systems (see chapter 10 for details). Participant's study information will not be released to anybody outside the medical team, except as necessary (and under confidentiality agreement) for the independent monitoring, auditing and for inspection by competent authorities.

During or after final publication of results, individual patient data might be shared for secondary research in an access-controlled way and on an anonymized basis, in line with the requirements that are currently being set up.

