4.5. Withdrawal and termination of the study

Reasons for withdrawal

Participants may be withdrawn from the study if:

- The parents/guardians of the participant withdraw the consent
- The participant develops epilepsy, psychiatric illness or severe gastric intolerance, or any other illness that could have a negative effect on the participant's health before the last dose of study medication
- The participant has vomited the initial and repeated dose of study medication
- The participant needs to get started on chronic medication for any reason before the last dose of study medication

Participants will only be considered lost-to-follow up after the week 48 follow-up visit window has passed. Participants who miss one or more study visits will remain in the study. The missed visits will be skipped, and the participant will continue with the original visit schedule (see chapter 5). Participants will be actively followed-up to attend all study visits.

Handling of Withdrawals

Participants withdrawing for medical reasons will be referred to adequate health facilities for further care if necessary.

Unless consent is withdrawn, efforts will be made to schedule, for these participants, at least the week 24 and week 48 follow-up visits. Collection and follow-up of adverse events and serious adverse events is further described in chapter 7.

Participants who have been withdrawn from the study will be offered a standard dose of PZQ.

Data collected up to the time of withdrawal will remain in the study data base and be used for analysis whether or not the participant continues with the follow-up visits.

Termination of study

In case the members of the DSMB (see chapter 7.2), based on preliminary data presented to them, show concern about the continuation of the trial (for safety or any other reason) they may collectively advice the Sponsor to prematurely terminate the study. Following ethical shortcomings in the conduct of the project, the ethics committees in Senegal or Belgium could also decide to stop the study.

If the study is prematurely terminated or suspended, the Sponsor will promptly inform the investigators/institutions, and the regulatory authority(ies) of the termination or suspension and the reason(s) for the termination or suspension. The ECs will also be informed promptly and provided the reason(s) for the termination or suspension by the Sponsor or by the investigator/institution, as specified by the applicable regulatory requirement(s).

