6. STUDY INVESTIGATIONAL PRODUCT

6.1. Purchasing and administration

The investigational fixed drug combination artesunate-mefloquine (AM) as well as praziquantel (PZQ), manufactured by the Indian company Cipla, will be used for the study. Both drugs received WHO prequalification. The drugs will be donated by the company. In any way, the company will not intervene in the design of the study, nor in the analysis and dissemination of the results).

The Investigational Medicinal Products (IMP) will be shipped directly from the manufacturer to the study site, following the good distribution practices.

Praziquantel is available in a formulation of 600 mg per tablet and will be administered as a single dose, adjusted according to the weight of the participant with a best approximation to the target dose of 40 mg/kg.

Participant's weight	Number of Praziquantel tablets
≥12 - <19kg	1
≥19 - <27kg	1 ½
≥27 - <34kg	2
≥34 - <42kg	2 1/2
≥42kg	3

The investigational AM combination is available in two fixed dose formulations, e.g. artesunate-mefloquine 25/50 mg and artesunate-mefloquine 100/200 mg.

The recommended target dose for each drug is 4 mg/kg for artesunate and 8 mg/kg for mefloquine per day given once day for three days, corresponding to total doses of 12 mg/kg and 24 mg/kg, respectively. The dose should be adjusted according to the weight of the participant.

Participant's weight	Number of artesunate-mefloquine tablets
≥15 – <22kg	3 25/50mg tablets/day
≥22 – <28kg	1 100/200mg tablet/day
≥28 – <34kg	1 100/200mg tablet + 1 25/50mg tablet/day
≥34 – <40kg	1 100/200mg tablet + 2 25/50mg tablets/day
≥40 – <47kg	1 100/200mg tablet + 3 25/50mg tablets/day
≥47kg	2 100/200mg tablets/day

The participant is followed up for at least 30 minutes after administration of AM and PZQ. If vomiting occurs within 30 minutes of drug administration, the full daily dose should be repeated. If vomiting occurs more than 30 minutes after dosing, half the recommended daily dose should be given. If the repeat dose is vomited, treatment should be discontinued, and the patient is withdrawn from the trial. The administration of AM may be delayed, as long as the three doses are given within a maximum of 5 days. The administration of one of the dose will be cancelled if it is not feasible to organize the administration outside of this period. Children that did not receive a full treatment administration will stay in the study and be followed up as planned.

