11.7. Compensation

Study participants will receive no financial compensation. However, all examinations that are described in the trial are performed free of charge. Children that are diagnosed with schistosomiasis but are not eligible for the trial because of the presence of exclusion criteria or because their parents or guardian did not consent (or the children themselves did not assent) will be treated with PZQ according to WHO guidelines. AEs and SAEs will be managed according to specific SOP's. In case of severe intolerance (digestive or neurological), treatment will be discontinued, and the child concerned will be withdrawn from the trial and treated and followed up through regular health care facilities until adverse symptoms subside.

Moreover, the trial budget will cover the costs of transportation to the hospital if the children would be referred to the reference hospital for further examination and case management. In some cases, the trial budget may contribute to fees for hospital care and medication for study participants.

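### Stopping study drug for a vomited repeat dose or severe intolerance also ends trial participation, so the week 4 sample behind the supporting ITT cure rate is not secured

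*Protocol*

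**What the plan says.** Three places in the protocol tie stopping drug to leaving the trial.

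- Section 6.1, vomiting: "If the repeat dose is vomited, treatment should be discontinued, and the patient is withdrawn from the trial".
- Section 11.6.1, intolerance: "In case of severe intolerance (digestive or neurological), treatment will be discontinued, and the child concerned will be excluded from the trial".
- Section 11.7, same event: "the child concerned will be withdrawn from the trial and treated and followed up through regular health care facilities until adverse symptoms subside".

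Section 4.5 covers what happens next. On visits: "Unless consent is withdrawn, efforts will be made to schedule, for these participants, at least the week 24 and week 48 follow-up visits". On rescue treatment: "Participants who have been withdrawn from the study will be offered a standard dose of PZQ". No time is given for that dose.

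The primary efficacy endpoint is microscopic cure at week 4 (sections 2.1 and 8.2). The per-protocol set is primary and ITT supports it; the ITT set is meant to hold children whose AM dosing was incomplete or out of window (section 8.3.1). Nothing is imputed (section 8.3.6).

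**The concern.** Coming off drug and coming off study are different events, and the protocol merges them for children who tolerate the drug badly. A child withdrawn during course 1 has no stated route to the week 4 sample. If the withdrawal dose of PZQ is given before week 4, a sample that is taken reflects the comparator as well as AM.

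The reason for the loss is treatment-related. Section 11.6.1 describes mefloquine toxicity as early and acute, and course 1 has three dosing days under AM against one under PZQ, so such losses would plausibly fall more in the AM arm and before week 4. The per-protocol set generally leaves these children out by design. The ITT analysis is there to show whether that exclusion matters, and it cannot do so if the same children have no usable outcome. An analysis plan cannot recover a sample that was not collected.

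**Working it through.** **Setting the plan's own figure.** Section 4.3 asks for 300 evaluable children per arm. With 75% cure in both arms, a 10-point margin, one-sided 0.025 and 80% power:

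n = 2 x 0.75 x 0.25 x (1.960 + 0.842)^2 / 0.10^2, which rounds up to 295 per arm.

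This agrees with 300 to within 3%, so 75% and 10 points are the right scale for what follows.

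**Which withdrawals matter.** Only course 1 events precede week 4. Courses 2 and 3 start at weeks 6 and 12.

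**Inputs.**
- AM arm: 363 recruited (section 4.3).
- Share w of AM children withdrawn before week 4: not given. I assume 1% and 2%, borrowing the AE frequency that section 1.1.1 cites from malaria treatment, with 5% as an upper case. That figure counts adverse events, not withdrawals. 363 x 0.01 = 3.6, 363 x 0.02 = 7.3, 363 x 0.05 = 18.2, so about 4, 7 and 18 children.
- True AM cure rate p: 75% or 65%.
- Cure rate c among the withdrawn: not given. c = 0 is the extreme.
- PZQ loss: set to zero, which is the assumption least favourable to the plan.

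**Handling A: unsampled children are dropped.** Observed AM rate = (p - w x c) / (1 - w).

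| w | p = 75%, c = 0 | p = 65%, c = 0 |
|---|---|---|
| 1% | 75.76% (+0.76 points) | 65.66% (+0.66) |
| 2% | 76.53% (+1.53) | 66.33% (+1.33) |
| 5% | 78.95% (+3.95) | 68.42% (+3.42) |

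With c = p the shift is zero. Intermediate c gives less: at p = 75%, w = 2% and c = 40%, (0.75 - 0.008) / 0.98 = 75.71%, a shift of +0.71.

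**Handling B: unsampled children stay in the denominator and are not counted as cured.** Observed AM rate = p - w x c. With c = 0 the shift is zero. With w = 2% and c = 40% it is -0.02 x 0.40 = -0.8 points, against AM.

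**When Handling A could change the conclusion.** Take PZQ 225/300 and four uncured AM children missing, with a Wilson-based hybrid score interval for the difference (section 8.3.3 names Wilson's method).

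| AM cures | Lower limit, of 300 | Lower limit, of 296 |
|---|---|---|
| 213 | -11.05 | -10.09 |
| 214 | -10.71 | -9.74 |
| 215 | -10.36 | -9.39 |
| 216 | -10.02 | -9.04 |
| 217 | -9.68 | -8.69 |

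The ITT conclusion flips only at 214, 215 or 216 cures. At 213 both versions fail; at 217 both succeed.

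**The case against.** The strongest objection concerns the ITT denominator. Section 8.2 divides the cured by everyone in the arm, and section 8.3.6 excludes missing subjects from the per-protocol analysis without saying that ITT drops them. Read that way, Handling B applies and nothing is inflated in AM's favour. The rule against imputation sits awkwardly with that reading, so the handling is open and may be settled in the analysis plan. This stands. A reader might infer that the withdrawal rules bias the trial towards non-inferiority; the protocol does not support that, because the direction depends on a rule it does not fix.

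Other parts of the case also stand. The vomiting rule in section 6.1 applies to both drugs, and vomiting is a listed PZQ effect, so PZQ losses would offset part of any shift. Section 4.5 sets a floor for visits and does not forbid week 4. Section 7.1 plans an AE contact four weeks after each administration, which for course 1 is the sampling visit in section 5.1, so the child may well be seen; but no text says the sample is then taken. Concomitant-medication checks could reveal an early PZQ dose, though they would not restore the sample.

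A reader might also infer that section 6.1 contradicts itself, since it says "Children that did not receive a full treatment administration will stay in the study and be followed up as planned". That sentence follows the rule for cancelling a dose that cannot be given within five days, so vomiting can be read as a specific exception. There is some tension, but it is not a clear contradiction.

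Finally, a reader might infer a safety error because sections 11.6.1 and 11.7 name digestive and neurological but not psychiatric intolerance, whereas section 4.5 has psychiatric illness only under "Participants may be withdrawn from the study if". That list reads "The participant develops epilepsy, psychiatric illness or severe gastric intolerance" and also includes repeat vomiting and withdrawn consent, so its opening verb does not give psychiatric illness a lower status. Section 11.6.1 further provides for discontinuation on medical decision and assessment before each later AM course, and section 3 for DSMB review before each. The missing word is at most an inconsistency of wording.

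**Conclusion.** The point holds in limited form. Following sections 6.1, 11.6.1, 11.7 and 4.5 as written can lose the week 4 sample, or let it follow PZQ, for a child who stops drug in course 1 for a treatment-related reason. The per-protocol primary result is largely unaffected; the supporting ITT cure rate is what suffers.

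The effect is probably small. At an assumed 1-2% AM-only loss with none cured, dropping the children raises the AM rate by about 0.7-1.5 points against a 10-point margin, and by 3.4-3.9 points at the 5% upper case. It is less if some are cured or PZQ children are lost too. Keeping them in the denominator gives no inflation, and any error goes against AM. The conclusion would change only in a narrow band near the margin. The protocol gives neither the withdrawal rate nor the cure rate of these children, so these sizes are illustrations. This is a cheap improvement to conduct, not a flaw in the primary analysis.

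**What to change.** In section 4.5, with matching wording in sections 6.1, 11.6.1 and 11.7, state that:

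1. A vomited repeat dose or severe digestive or neurological intolerance stops the current and all later study drug, and does not end follow-up.
2. Week 4 stool and urine sampling and all later scheduled visits continue unless consent is withdrawn.
3. PZQ is offered after the week 4 sample, or earlier on clinical need, and its date is recorded.

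Optionally, add psychiatric reactions to the parenthesis in sections 11.6.1 and 11.7 so that it matches section 4.5.

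The cost is protocol and SOP wording. The visits already exist and the sample size does not change. The downside is a short delay of PZQ for a few children, limited by the clinical-need clause.
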